Study Protocol and Statistical Analysis Plan

Evaluation of Extended Wear Technology

V 2.0

December 20, 2021

NCT04882800

Evaluation of Extended Wear Technology

1 Background

Since its original launch in 2008, the Lyric device has offered hearing impaired patients an invisible and more convenient option when compared to conventional daily wear hearing aids. Designed to be worn in the ear canal for several weeks or months at a time, this extended wear, non-custom hearing aid has gone through several iterations and product improvements in the last decade. These product improvements included an expanded size offering in 2017. However, even with this expanded size offering, discomfort, migration, feedback and sound quality still account for a large number of trial cancellations. These issues are often caused by a less than ideal fit, especially if a patient has narrowing ear canal.

2 Objectives

The primary objective is to determine if patients who have rejected or cancelled Lyric subscriptions within the last two years due to discomfort or feedback, migration or poor sound quality (due to poor fit) rate the investigational Lyric4 devices with a fitting modification as more comfortable than the conventional Lyric4 devices.

There are no secondary objectives.

3 Description of the investigational device

The Lyric4 device is an analog hearing instrument that is deeply inserted in the ear canal. It consists of an electronic module and two seals, a medial and lateral, glued onto the electronic module. Currently, the Lyric4 is available in seven non-custom sizes: XXS, XS, S, M, L, XL, and XXL. The investigational device is made of the same components of the commercially available Lyric4 device, but with a fitting modification which may allow for an improved fit for narrower ear canals and increase the size options.

4 Design of the clinical investigation

This will be an interventional, single group design with two conditions (Lyric4 and Lyric4 with fitting modification) where subjects will wear the currently available Lyric device in one ear and the investigational device in the opposite ear for two weeks; and then switch ears for two additional weeks. Subjects will be blinded as to which device is in each ear.

5 Risks and benefits of the investigational device and clinical Investigation

The product-related risks and the clinical investigation procedure-related risks are well-controlled during the clinical investigation as the subject is under the care of a well-established, Lyric-trained, hearing health care provider. Any ear health risk from this investigation is no greater than any risk a hearing impaired patient experiences when undergoing a Lyric trial with a certified Lyric provider.

The study may reveal that the investigational devices are more comfortable for those patients who were unable to wear Lyric devices previously, thus implying an improved fit rate. The investigational devices are not custom, and do not require extensive modifications of the Lyric component itself. If improved fit rate can be confirmed, it is

likely that more hearing impaired patients who would like to experience the benefits of an extended wear device would be able to do so.

6 Endpoints

To satisfy the primary objective, subjective questionnaires will be administered after each device fitting and removal. Question domains may include, but are not limited to, comfort, occlusion, feedback, sound quality, and purchasing interest.

7 Inclusion and Exclusion Criteria

Inclusion criteria: Hearing loss N2-N4 (mild to moderate)

Hearing impairment: Any (conductive or sensorineural)

Population: Adults

Minimum Age: 18 years

Maximum Age: 90 years

Other: Previous Lyric users who rejected or cancelled Lyric trials or subscriptions due to discomfort, feedback, migration, or poor sound quality due to fit issues.

Exclusion criteria: Participants who can only wear a size XXS Lyric will be excluded as even an XXS investigational device would likely not be any more beneficial than a conventional XXS Lyric4 device.

Asymmetrical hearing loss

Other diagnosis that may cause fluctuations in hearing (i.e. Meniere's disease)

Unable to tolerate the physical fit of a Lyric device

Inability to be seen for 4 lab visits

8 Measurements and procedures

Investigation related procedures:

Study Procedure	Impact on subject	Standard of care?
Audiogram; may be done if most recent audiogram is more than 12 months old	Assesses hearing loss	Yes
Cerumen management	Clears ear canal of wax	Yes
Ear mold impression; may be done for future analysis of ear shape	Takes custom impression of ear	Yes

Fit with Lyric devices	Provides prescriptive amplification	Yes
Questionnaires; will be completed after each home trial for both devices	Assesses subjective relating to the investigational device/feature	No –These questionnaires were designed for this specific study. They are not validated for clinical outcomes.

All analysis of the results will occur at the conclusion of the study. All study data will be stored digitally. The data will be collected from the participants using paper questionnaires and then be stored in an excel file for analysis. Collection of the questionnaire results will occur on an ongoing basis. The lead investigator will scan the paper questionnaires and send them to the study manager via email. All original copies of the questionnaires will be stored at the investigation site until the conclusion of the study, at which point they will be mailed to the study manager. Only authorized research personnel at the sponsor site will have access to the study results.

9 Statistical design and analysis

A priori sample size estimation was not performed for this investigation, as the investigation is exploratory and does not aim to confirm any effect with statistical significance and power.

This is an exploratory trial and will not have statistical criteria for termination.

The experiment performed within this study is designed to evaluate the efficacy and effectiveness of new fitting characteristics to the Lyric extended-wear hearing technology as compared to the commercially available Lyric device. The statistical hypothesis is that average ratings of wearing comfort with the new technology will be equivalent to or better than the commercially available technology. A qualitative analysis of the questionnaires will be used for data analysis. Qualitative data will be collected as a question, response, and anonymous participant ID for all participants at each device fitting and removal.

Due to the exploratory nature of this investigation, an informal exploration of the data will be performed at the conclusion of the trial. No further statistical analysis is planned.

All safety related events will be constantly monitored by the investigators and will immediately reported to the Principle Investigator. Evaluation of any SAE, SADE, or UADE will be conducted promptly using Sonova's standard medical device referral protocol. Confirmed UADEs will be reported to the IRB within 10 days after receiving notice of the event. If it is determined that an event or effect presents an unreasonable risk to subjects, this study, or those parts of the study presenting that risk, will be terminated no later than 5 working days after the determination is made and no later than 15 working days after Sonova USA first received notice of the event.

A safety analysis of the relevant data will be done after the data collection is finished.

Deviations to the statistical plan will be captured and reported in an update to this document, with justification.

If data records are complete from subjects who dropped out of the study early, these data will also be used in the analysis. If the data sets are not complete, they will not be integrated at all. If a subject is dropping out before data collection is finished, the study team will try to complete as many data sets as possible. If a subject drops out before the first study visit the subject will be replaced if possible.

10 Investigation Duration

The investigation is expected to last approximately 8 weeks. The expected duration for participation by the subjects is 4-5 weeks.

11 Data Handling and Management

Study data is recorded both with paper and with electronic Case Report Forms (p/eCRF). For each enrolled study participant a CRF is maintained. All CRFs are kept current to reflect the subject's status at each phase during the course of study. Participants cannot be identified in the CRF by name or initials and birth date but an appropriate coded identification is used. All study team members are authorized for the CRF entries and it is assured that any authorized person can be identified both for pCRFs and eCRFs. If pCRFs are used, the investigator's acronym as well as the subject ID is filled in and data are entered into an electronic file for analysis by the respective investigator and data get monitored by the assigned monitor. In case of a self-evident corrections, either the subject does it by himself or the investigator undertakes the correction by crossing out the word/sentence with a single horizontal line and by adding the correction including his personal identifier and the date.

Source documents for this investigation include, audiograms, ALPs fitting files, Lyric history, including prior adverse events, appointment checklists, and paper copies of the subjective questionnaires.

All paper data will be stored in a locked filing cabinet at the Phonak Audiology Research Center (PARC). All electronic data files will be encrypted and stored on secure research computers. All identifying data will be stored at the site. De-identified data will be shared, if necessary, with production to cross-check the quality of scans/impressions, and with partners at Sonova Switzerland.

The identifiable data will be destroyed as soon as the final analyses have been completed. The de-identified data will be kept for seven years after the publication of results. When the data are destroyed, paper records will be shredded by services provided at PARC. Electronic data will be encrypted as de-identified NOAH packages, where applicable, to be shared with Sonova Switzerland.

12 Amendments to the CIP

Amendments to the study plan, if necessary, will be updated with justification in this document.

13 Deviations from clinical investigation plan

Deviations from the study plan to protect the rights, safety and well-being of human participants under emergency circumstances may proceed without prior approval of the sponsor and the EC – such deviations will be documented and reported to the sponsor representative (Study Manager) and the EC as soon as possible. Apart from that the investigator is not allowed to deviate from this study plan unless that deviation does not influence the investigation data.

14 Device accountability

The sub-investigator at site or authorized designee will keep records documenting the following in a written process:

- Names of participants who received, used, returned, or disposed of device
- Date of receipt, identification, and quantity of each investigational device (batch/serial number or unique code)
- Expiry date (if applicable)
- Date(s) of use
- Participant identification

15 Informed consent process

At the beginning of the first appointment, the investigator will hand the consent form to the participant in a private setting and grant sufficient time to read the whole form. The consent form contains detailed information about incentives and reimbursement. Any questions will be answered and the participant will be given sufficient time to decide whether or not they want to participate in the study. After the participant signed two copies of the consent form, the researcher will sign both copies as well and provide one copy to the participant.

In case of changes to the procedures described in the consent form, the participant will be informed at the beginning of an appointment.

Informed Consent will only be obtained by investigation participants who can provide informed consent themselves before enrollment.

16 Adverse events, adverse device effects and device deficiencies

Device deficiencies and all **adverse events (AE)** including all **serious adverse events (SAE)** are collected, fully investigated and documented in the source document and appropriate case report form (CRF) during the entire investigation period, i.e. from participant's informed consent until the last protocol-specific procedure, including a safety follow-up period (ISO_14155, 2020)

Evaluation of any SAE, SADE, or UADE will be conducted promptly using Sonova's standard medical device referral protocol.

In the event of an adverse event, the investigation manager will make contact with the principal investigator within 24 hours to align on reporting procedures and to evaluate the relationship of the investigational device and the related procedure.

In the event of a serious adverse event, this will be reported to the FDA using Reporting Form FDA 3500, or by telephone at [name].

Confirmed UADEs will be reported to the IRB within 10 days after receiving notice of the event. If it is determined that an event or effect presents an unreasonable risk to subjects, this study, or those parts of the study presenting that risk, will be terminated no later than 5 working days after the determination is made and no later than 15 working days after Sonova USA first received notice of the event.

A causal relationship towards the medical device or investigation procedure should be rated as follows:

Not related: The relationship to the device or procedures can be excluded.

Unlikely: The relationship with the use of the device seems not relevant and/or the event can be reasonably explained by another cause, but additional information may be obtained.

Possible: The relationship with the use of the investigational device is weak but cannot be ruled out completely. Alternative causes are also possible.

Probable: The relationship with the use of the investigational device seems relevant and/or the event cannot be reasonably explained by another cause.

Causal relationship: The serious event is associated with the investigational device or with procedures beyond reasonable doubt.

Device deficiencies that might have led to an SAE are always related to the medical device.

The causality assessment of the SAE will be conducted according to MDCG 2020-10/1 Safety Reporting in Clinical Investigations of Medical Devices under Regulation (EU) 2017/745.

The reporting of Serious Adverse Events and Device Deficiencies follows the Regulation (EU) 2017/745 and the MDCG 2020-10/1 Safety Reporting in Clinical Investigations of Medical Devices under Regulation (EU) 2017/745.

17 Vulnerable Populations

The investigation does not include any vulnerable populations.

18 Suspension or premature termination of the clinical investigation

The clinical investigation will be suspended or prematurely terminated if the feature and/or investigative device malfunctions or if the participants or researchers are exposed to safety risks other than those outlined in this document. These events may include but are not limited to – natural disaster, widespread outbreak of illness, compromised structure of the investigation site, etc.

19 Publication policy

The clinical investigation will be registered in clinicaltrials.gov, a publicly accessible database, as required by US law.

The results of the clinical investigation will be documented internally in a study report with the possibility of an online publication.

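### Only subjects are blinded: nothing masks the person who codes and summarises the questionnaires, although that step is a qualitative, informal reading

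*Combined protocol and SAP*

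**What the plan says.** Section 4 describes a within-subject comparison: the conventional device in one ear, the modified device in the other, and a switch of ears after two weeks. On masking it says only: "Subjects will be blinded as to which device is in each ear". No other role is named as blinded, there or elsewhere.

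The outcome is subjective. Section 8 says of the study-specific questionnaires: "They are not validated for clinical outcomes". Section 9 states the hypothesis that "average ratings of wearing comfort with the new technology will be equivalent to or better than the commercially available technology", with no margin. On method it says: "A qualitative analysis of the questionnaires will be used for data analysis". It then closes the matter: "an informal exploration of the data will be performed at the conclusion of the trial. No further statistical analysis is planned".

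On data flow, Section 8 says: "The lead investigator will scan the paper questionnaires and send them to the study manager via email". The answers go into an Excel file, all analysis takes place once at study end, and access to the results is limited to approved sponsor research staff. Section 9 lists the recorded items as question, answer and a coded participant number. Section 11 adds that, where paper case report forms are used, the investigator concerned enters the data into the file used for analysis.

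**The concern.** Blinding the subject protects the answer that is given. It does not protect what happens to that answer afterwards: how a comment is classified, which answers are emphasised, and how a mixed set of replies is summed up. A pre-specified numerical summary leaves little room for this. A qualitative, informal reading leaves a good deal, because nothing fixed in advance limits the reader's judgement.

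The access rule in Section 8 implies that the reader works for the device's sponsor. If that person also knows which answers belong to the modified device, unclear replies can be resolved in its favour without any intent to mislead. What is at stake is the answer to the study's only objective, whether subjects rate the modified device as more comfortable. Varying the starting ear would not remove this problem, because it arises after the data are collected.

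**Working it through.** The plan gives no sample size, rating scale, standard deviation, margin or error rate, so there is no figure to reproduce. The check sets the relevant sections side by side.

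1. **Who is masked.** Section 4 names subjects. Sections 8, 9 and 11 mention the lead investigator, the study manager, sponsor staff with access to results, and the investigator who enters form data. None of them is described as masked.

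2. **Is the device label coded?** The items listed in Section 9 include no device label at all. A comparison of two devices cannot be made without one, so a label must be attached somewhere. The plan says neither when, nor by whom, nor whether it is open or coded.

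3. **How much judgement does the analysis allow?** The hypothesis concerns average comfort ratings, but the planned method is qualitative and informal. No average, paired difference, coding frame or decision rule is laid down. Section 9 also leaves out incomplete data sets without defining completeness, which is a further decision that someone could make with the device known.

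4. **Can this step be masked?** Yes, on the described flow. Forms already pass from the lead investigator to the study manager, participants already carry coded numbers, and no analysis occurs before study end, so no planned reading needs the labels earlier. The weak point is Section 11: if the investigator who fits the devices also builds the analysis file, withholding a code when the scans are emailed achieves nothing unless entry is verbatim and the labels in the file are neutral.

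5. **Which label would mask?** Each subject contributes 2 ears × 2 periods = 4 ear-by-period cells, two of them with the modified device. Section 4 does not say how the starting ear is chosen.
   - If it is the same for everyone, the same two cells hold the modified device in every subject. Ear and period then give the device away throughout.
   - If it varies and the assignment is withheld, ear and period do not reveal the device.
   - A neutral code set separately for each subject (device A and device B, with the meaning of A differing between subjects) masks in either case, provided that ear and period are left out of the reader's file when the starting ear is fixed. It still allows the within-subject comparison.

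**The case against.** The strongest reply is that this is a gap of silence. A reader might infer that sponsor staff will read the answers under known device labels. The documents do not say so: the analyst is not identified, and the listed items contain no device label. What can be said is that the plan provides no masking at this step, not that it plans an open reading.

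Second, a numerical rating chosen by a blinded subject leaves little to interpret, and the questionnaire itself is not in the documents. Free-text answers are made plausible by the qualitative method but are not described. This limits the concern. Fixing a numerical comfort summary in advance would remove much of the reader's discretion and is worth doing, but it would not protect any reading of free text.

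Third, a reader might want to put a size on the bias. That would need the share of answers open to interpretation and the fraction of those resolved towards the modified device. Neither is in the documents. If no answers are open, or if open answers are resolved evenly, the bias is zero. A calculation in terms of preference would also address a quantity other than the average ratings named in the hypothesis.

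Fourth, the study is declared exploratory, with no confirmatory aim. That removes any claim about error rates or power. It does not remove the value of an even-handed reading, since Section 5 looks ahead to what would follow if a better fit rate were confirmed.

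**Conclusion.** The point holds as a gap in protection. Subjects are the only masked party, the analysis depends on judgement, and nothing prevents the person making that judgement from knowing the device. The conclusion on comfort could be tilted as a result, in a direction and by an amount that cannot be estimated from the documents.

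This rests on two assumptions: that a device label will be available to the reader, which the comparison requires in some form, and that the answers leave something to interpret, which the choice of a qualitative method suggests. The change is advisable and inexpensive. The plan's exploratory status keeps it below an essential correction.

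**What to change.** Amend Sections 4, 8, 9 and 11 together:

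- **Section 4:** state which roles besides the subjects are masked, and say whether the starting ear varies between subjects.
- **Section 8:** label the questionnaires and the Excel file with the subject number and a neutral per-subject device code. Use ear and period as labels only if the starting ear varies between subjects and the assignment is withheld from the reader.
- **Section 9:** the sponsor's reader codes and summarises the responses without the key. The key stays at the fitting site and is released only after the ratings and the free-text coding are locked. How the per-subject summaries will be combined is written down before release. Unmasking is allowed for adverse event assessment.
- **Section 11:** any data entry by the investigator is verbatim, with classification of answers left to the masked reader.

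The cost is protocol wording, upkeep of a key at the site and a lock step before its release. The documents do not describe staffing, so the sponsor should confirm that the reader is not also the person who fits the devices or assigns the codes. The reader has no device labels until lock. Masking will be imperfect if a free-text answer reveals the device, or if the reader is drawn into adverse event handling: under Section 16 the investigation manager takes part in judging whether an event is related to the investigational device.

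### Section 5 infers an improved fit rate from comfort ratings, but fitting success and two-week retention are neither defined nor analysed, and the complete-data rule may drop the failures

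*Combined protocol and SAP*

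**What the plan says.** Section 5 (risks and benefits) says the investigational devices may turn out to be "more comfortable for those patients who were unable to wear Lyric devices previously, thus implying an improved fit rate". It continues with "If improved fit rate can be confirmed", in which case more hearing-impaired patients would probably be able to use an extended-wear device.

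The rest of the plan concerns comfort:

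- **Section 2:** the primary objective is whether patients "rate the investigational Lyric4 devices with a fitting modification as more comfortable than the conventional Lyric4 devices". It adds: "There are no secondary objectives".
- **Section 4:** each subject wears one device in each ear "for two weeks; and then switch ears for two additional weeks". That makes four wears per subject, two with each device.
- **Section 6:** the endpoint is that "subjective questionnaires will be administered after each device fitting and removal". The topics they cover are left open: "Question domains may include, but are not limited to, comfort, occlusion, feedback, sound quality, and purchasing interest".
- **Section 8:** the procedures table has questionnaires completed after each home trial, for both devices.
- **Section 9:** the hypothesis is about average comfort ratings. The analysis is an informal, qualitative exploration and nothing further is planned. On missing data: "If the data sets are not complete, they will not be integrated at all". The adjoining sentences keep complete records from subjects who leave early and commit the team to completing as many data sets as it can.

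**The concern.** Comfort is how a device feels to someone wearing it. A fit rate is the share of attempted fittings in which the device can be placed and kept in. The plan passes from the first to the second without defining or measuring the second. Sections 1 and 3 motivate the modification by trial cancellations linked to poor fit, so readers of the study report will look for evidence on fit.

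The trial will generate that evidence. With one device in each ear, a subject whose conventional device comes out early while the investigational one stays in (or the reverse) is a direct within-person comparison. No analysis uses it. If an early removal leaves the data set incomplete, the whole subject may be dropped, and with it the data from the device that stayed in.

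**Working it through.** **1. Is fit rate measured anywhere?** Setting the sections side by side, it is not in the objective (Section 2), the named questionnaire domains (Section 6), the hypothesis or the analysis (Section 9), and it has no definition. The domain list is open-ended, but nothing in it commits the study to recording fitting success or retention as an outcome. This gap does not depend on how missing data are handled: even with no subject dropped, a mean comfort rating is not a fit rate.

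**2. Does the complete-data rule remove fit failures?** The text does not settle it. Under Section 6, a removal triggers a questionnaire, so an early removal could still give a full set. Under the Section 8 wording, it is unclear whether an interrupted home trial gives one. Section 9 does not define completeness.

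**3. What could be at stake?** The plan states no sample size, rate, margin or SD, so there is no figure of its own to reproduce. Every input below is an assumption.

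*Inputs:* 0–10 comfort ratings, normal, with mean 5 (conventional) and 6 (investigational). Between-subject SD is 1.2 and within-subject SD 1.6. A device is removed early when its rating is at or below a cut-off c. All four wears must succeed for the set to be complete.

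*Retention per wear.* Total SD = √(1.2² + 1.6²) = √(1.44 + 2.56) = 2.0. Retention = Φ((mean − c)/2.0).

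- c = 3: Φ(1.00) = 84.1% versus Φ(1.50) = 93.3%.
- c = 2.5: Φ(1.25) = 89.4% versus Φ(1.75) = 96.0%.

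*Share complete.* With subject effect u ~ N(0, 1.2²), the share is the average over u of [Φ((5 + u − c)/1.6) × Φ((6 + u − c)/1.6)]².

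*Comfort gain among complete subjects.* Given u, the mean rating of a retained device is m + u + 1.6·φ(a)/(1 − Φ(a)), where m is the device mean and a = (c − m − u)/1.6. The difference between devices is averaged over u, weighted by the probability of being complete.

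Numerical integration gives:

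| Cut-off | Retention, conventional / investigational | Complete | Comfort gain (true 1.0) |
|---|---|---|---|
| 3 | 84% / 93% | 68% | 0.82 |
| 2.5 | 89% / 96% | 78% | 0.86 |

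(The last gain is 0.8646 unrounded; simulation gave 0.86 to 0.87.) In both rows, retention among the analysed subjects is 100% for each device, so the true gap cannot be seen.

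*If only some failures are dropped.* Let a random half of the subjects with any failed wear still give complete data, at c = 3. The share kept is 0.678 + 0.5 × (1 − 0.678) = 0.839. The visible retention gap is 0.5 × (0.933 − 0.841)/0.839 = 0.055, about 5 points against a true 9. If all such subjects give complete data, the gap and the comfort gain are both unbiased.

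*Range over other assumed retention rates.* With independent wears, the complete share is (p_conventional × p_investigational)²: (0.90 × 0.95)² = 73%, (0.80 × 0.90)² = 52%, (0.70 × 0.85)² = 35% and (0.60 × 0.80)² = 23%. With a within-subject correlation of 0.5, simulation gives 79%, 63%, 50% and 39%.

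**The case against.** The strongest reply is that Section 5 is a conditional statement of possible benefit. The study calls itself exploratory, its only objective is comfort, and that objective needs no fit-rate analysis. This stands. A reader might infer that an improved fit rate is a conclusion the study is designed to reach, and the documents do not say so. The exploratory label excuses the lack of power, though. It does not support inferring an outcome that is not measured.

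A reader might also infer that the missing-data rule removes every fit failure, so that retention is 100% in both arms by construction. The documents do not support this as fact. Complete records from early leavers are kept, the team tries to complete data sets, and Sections 6 and 9 attach data collection to each removal. Total exclusion is the worst case.

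Three further points have some force:

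- Comfort is not irrelevant to fit. Section 1 lists discomfort among the reasons for cancellation that are often caused by poor fit. Comfort is an imperfect proxy for fit and should be described as one.
- Section 7 excludes people unable to tolerate the physical fit of a Lyric device, which may make outright failures less common. The plan gives no rate.
- In the illustration the comfort gain shrinks towards zero and keeps its sign. It does not show a false claim of benefit, and the direction of the bias depends on the assumed model.

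**Conclusion.** The point holds in a limited form. Fit rate is undefined and unanalysed, so comfort ratings alone cannot confirm that it has improved. This rests on the text alone and needs no assumption. The complete-data rule may make matters worse by excluding failed fittings and early removals along with the paired device's data, but how often cannot be determined from the documents.

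If every early removal made the set incomplete, the illustration loses 22% to 32% of subjects, hides a retention gap of 7 to 9 points, and reports a comfort gain of 0.82 to 0.86 in place of 1.0. If failures still give complete data, the bias is nil. The comfort objective itself survives. This is a worthwhile and inexpensive improvement, not a fatal flaw.

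**What to change.** 1. In Sections 6 and 9, add one descriptive table. For every attempted fitting, by ear, period and device, it shows whether the device was placed and whether it was still in place at the planned two-week removal, with the date and reason for any earlier removal. All attempted fittings form the denominator, and the devices are compared descriptively within subject.
2. In Section 9, replace the complete-data rule: use all available ratings from these subjects, including the rating at an early removal, and do not drop the whole data set. Flag ratings taken before two weeks, because they reflect a shorter wear. Define completeness, and reconcile the questionnaire timing in Sections 6 and 8.
3. In Section 5, delete the clause that infers fit rate from comfort, and base any fit-rate statement on the new table.

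**Cost:** one extra table and no power calculation. Fitting files and appointment checklists are already source documents (Section 11). Section 14 logs dates of use, but as part of accountability for the investigational device, so the same dates would need to be recorded for the conventional device. If the sponsor does not want the table, the Section 5 deletion alone removes the unsupported inference, but the direct evidence on fit stays unused.
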